## 11.6.1 Excessive Toxicity

Excessive toxicity is defined as any adverse event that meets the following criteria:

- Any grade 3 or higher adverse event or an adverse event that leads to discontinuation of study therapy.
- The adverse event must be possibly, probably or definitely related to any of the study treatments (Ramucirumab, Oxaliplatin, Irinotecan, 5-FU)
- The adverse event occurs in the first four weeks of treatment
- The adverse event grade does not diminish to grade 1, four weeks after dose modification or dose delay. AE must have been adequately treated (e.g. nausea, vomiting, hematologic toxicities)

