# STATISTICAL CONSIDERATIONS

We aim to test the null hypothesis of PFS at 6 months. Using a one-sided log-rank test we have estimated a sample size of 85 patients (43 in one and 42 in another arm) which will provide 80% power under a type 1 error of 20%. This is an estimation on 24 months accrual and 9 months follow up after accrual for the primary endpoint. Sample size may increase to 95 to account for a 10% drop out rate.

The primary endpoint of this clinical trial is PFS. PFS is defined as the time from enrollment to the time of progression or death. An interim analysis with Kaplan Meier method and Logrank test will be conducted after 23 subjects have been enrolled in each arm and followed up for 9 months. The trial will stop if it detects a significant difference of 3 months in PFS between the study arm-mFOLFIRINOX/RAM, as compared to the standard arm-mFOLFIRINOX at the significance level of 0.0013 according to the O'Brien-Fleming approach. Otherwise the trial will continue until the targeted sample size has been completed.

RR, PFS and OS will be reported with 95% confidence intervals. Response is defined as a complete or partial response according to CT/MRI evaluations based on RECIST 1.1 criteria. Toxicity will be graded using CTCAE v4

**Early stopping:** In the case of excessive toxicity, safety-stopping rules will be used. A grade  $\geq 3$  or adverse event that will lead to stop or termination of treatment is defined as suspected treatment related toxicity observed in the first 4 weeks of enrollment after dose modification, but excluding: nausea or vomiting and hematologic toxicities if not adequately treated. Ramucirumab will be held for drug related adverse events grade  $\geq 3$  until recovery to grade  $\leq 1$  and then resumed with a lower dose level -1 (6 mg/kg). If the grade  $\geq 3$  related adverse events does not resolve within 3 weeks of holding treatment, subject will be taken off the trial. In the case of prolonged or medically concerning grade 2 toxicity related to chemotherapy combination, treatment will be interrupted until

[figure not shown]

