# 6.1.6 Conditions for permanent discontinuation of ramucirumab/placebo

Listed below are clinical conditions in which ramucirumab/placebo should be permanently discontinued.

- Grade 3 and 4 arterial thromboembolic events, or any PE/DVT occurring or
  worsening during anticoagulant therapy. Any arterial event leading to
  discontinuation of ramucirumab therapy will be considered serious and should be
  reported via the serious adverse event (SAE) mechanism.
- Subjects with Grade 4 hypertension must not receive further treatment with ramucirumab
- Gastrointestinal Perforation
- Grade 3 or 4 Bleeding
- Grade 3 or 4 Infusion Reaction
- Hepatic encephalopathy or other serious signs of liver impairment such as hepatorenal syndrome
- Fistula Formation
- Reversible Posterior Leukoencephalopathy (RPLS); All cases of RPLS must be reported via the SAE reporting guidelines.

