## 11.6 Excessive Toxicity – Criteria for Stopping and Interim Safety Analysis

In case of excessive toxicity, safety-stopping rules will be used. An acceptable toxicity rate will be assumed at 0.20. The study will be stopped based on an unacceptable excessive toxicity rate of 0.40. A sequential probability ratio test will be used where a likelihood ratio of 8 in favor of an excessive toxicity rate of 0.40 (vs. 0.20) provides sufficient evidence to stop the study due to excessive toxicity. Data will be continuously reviewed for excessive toxicity and statistical analysis performed if excessive toxicity is suspected. The table below provides the minimum number of patients exhibiting excessive toxicity that will trigger statistical analysis.

Total number of treated patients	Number of Patients observed with excessive toxicity
3	≥2
4-5	≥3
6-7	≥4
8-9	≥5
10-11	≥6
12-13	≥7
14-16	≥8
17-18	≥9
19-20	≥10

Version Date: 13AUG2018 Confidential Page 41 of 51

21-23	≥11
24-25	≥12
26-28	≥13
29-30	≥14
31-33	≥15
34-35	≥16
36-38	≥17
39-40	≥18

Ramucirumab will be held for drug related adverse events Grade  $\geq 3$  until recovery to Grade  $\leq 1$  and then resumed with a lower dose level -1 (6 mg/kg). If the Grade  $\geq 3$  related adverse event does not resolve within 4 weeks of holding treatment, the subject will be taken off study treatment.

In the case of prolonged or medically concerning Grade 2 toxicity related to the chemotherapy combination, treatment will be interrupted until recovery to Grade  $\leq 1$ , at which time treatment will be resumed at the same dose. If the adverse event does not resolve in or within 2 weeks with medical intervention, then the subject will be taken off study treatment.

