## 11.6.2 Interim Safety Analysis

The study will be closed to accrual and an interim safety analysis conducted after ten subjects are accrued to each arm. If the following rates of selected toxicities listed below are observed within the first cycle of treatment (four weeks), the regimen (Ramucirumab, Oxaliplatin, Irinotecan, 5-FU) will be considered toxic and the trial will be stopped.

Adverse Event (≥ grade 3)	Toxicity Rate (n/10 subjects)
Febrile Neutropenia	2/10
Peripheral Motor or Sensory Neuropathy	3/10
Hypertension	3/10
Life Threatening Thromboembolic Event	3/10
GI Perforation	2/10
Hemorrhage, Bleeding	2/10

Version Date: 13AUG2018 Confidential Page 42 of 51

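### The recovery condition in section 11.6.1 does not exempt events that permanently end ramucirumab/placebo, so such an event, once recovered, can be left out of the toxicity stopping rule

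*Combined protocol and SAP*

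**What the plan says.** Section 11.6 sets up a sequential probability ratio test of a toxicity rate of 0.40 against 0.20 ("An acceptable toxicity rate will be assumed at 0.20"). A likelihood ratio of 8 is sufficient evidence to stop. Section 11.6.1 says what is counted: "Excessive toxicity is defined as any adverse event that meets the following criteria". Four bullets follow:

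- "Any grade 3 or higher adverse event or an adverse event that leads to discontinuation of study therapy";
- at least a possible causal link to one of the four drugs in the regimen;
- onset in the first four weeks of treatment;
- "The adverse event grade does not diminish to grade 1, four weeks after dose modification or dose delay", followed by a sentence requiring adequate treatment of the event, with nausea, vomiting and hematologic toxicity as examples.

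Section 6.1.6 opens: "Listed below are clinical conditions in which ramucirumab/placebo should be permanently discontinued". Its list includes Grade 3-4 arterial thromboembolic events, GI perforation, Grade 3-4 bleeding, Grade 3-4 infusion reaction, fistula and reversible posterior leukoencephalopathy (RPLS). For these there is no step of holding and then reducing the dose.

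The synopsis (Statistical Considerations, Early stopping) describes a Grade 3 or higher event, or one that ends treatment, as "suspected treatment related toxicity observed in the first 4 weeks of enrollment after dose modification, but excluding: nausea or vomiting and hematologic toxicities", with a qualifier about adequate treatment. It then applies the same test: 0.20, 0.40, likelihood ratio 8.

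Section 11.6.2 adds one look after ten subjects per arm, with limits of 2/10 or 3/10 for six first-cycle event types and no recovery condition.

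**The concern.** The first criterion brings in events that end therapy. The fourth then asks whether the event has come down to grade 1 four weeks after a dose change or delay. That question suits toxicity managed by holding and reducing the dose. It suits poorly an acute event after which the drug is never given again. A Grade 4 infusion reaction may resolve within hours, and a Grade 3-4 bleed may resolve within four weeks. In both cases recovery says little about whether the regimen is safe.

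If such events are not counted, the 11.6 test does not move when they occur. After the 11.6.2 look it is the only toxicity rule with a numerical boundary. That look comes once and does not list infusion reaction, fistula or RPLS. What is at stake is safety monitoring of a VEGFR-2 antibody added to three-drug chemotherapy. The PFS comparison is not affected.

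**Working it through.** **Are the four criteria joint?** No *or* links the bullets. Read as alternatives, the second bullet alone would count any related Grade 1 event, and the Grade 3 threshold would do nothing. They have to be joint.

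**One event traced through the text.** Take a related Grade 4 infusion reaction in week 1, fully recovered, with ramucirumab/placebo permanently stopped under 6.1.6.

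- Criteria 1 to 3: met.
- Criterion 4, if a permanent stop is a dose modification (6.1.6 sits under the dose-modification section 6.1): the event fell to grade 1 in time, so it is not counted.
- Criterion 4, if a permanent stop is not a dose modification: the four-week clock has no start. Taken literally, the criterion is not met. It could also be read as not applying, in which case the event counts.
- Synopsis: no explicit recovery test, so the event appears to count.
- 11.6.2: infusion reaction is not listed.

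**The plan's own boundary.** LR(x, n) = (0.40/0.20)^x × (0.60/0.80)^(n−x) = 2^x × 0.75^(n−x). The smallest x with LR ≥ 8 is 3 of 3, 6 of 10, 8 of 20 and 14 of 40. The table in 11.6 has 2, 6, 10 and 18 at those sizes, and agrees with LR ≥ 8 at only 5 of its 38 sample sizes. That is a separate matter, since the table triggers analysis rather than stopping, but it is why results are given both ways below.

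**Size of the change.** The documents give no recovery share and no share of 6.1.6 events, so both are assumed:

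- p = 0.40, the true first-cycle rate of related Grade ≥3 events;
- r = share of these that recover in time;
- s = share of the recovered events that fall under 6.1.6.

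The counted rate is p(1 − r) under the literal text and p(1 − r + r·s) with a 6.1.6 exemption. Stopping probabilities come from exact binomial recursion with review after every subject up to 40. Take s = 0.10:

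| r | Counted rate, literal text | P(LR ≥ 8) | Counted rate with exemption | P(LR ≥ 8) |
|---|---|---|---|---|
| 0.25 | 0.40 × 0.75 = 0.30 | 45.8% | 0.40 × 0.775 = 0.31 | 50.7% |
| 0.50 | 0.40 × 0.50 = 0.20 | 8.5% | 0.40 × 0.55 = 0.22 | 13.3% |
| 0.75 | 0.40 × 0.25 = 0.10 | 0.3% | 0.40 × 0.325 = 0.13 | 1.1% |

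If the table count must also be reached, the three rows become 19.9% to 22.8%, 3.8% to 5.6%, and 0.3% to 0.7%.

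**Dropping the recovery condition for every event.** The chance of stopping by 40 subjects would then be 8.5%, 23.2% or 45.8% at a background rate of 0.20, 0.25 or 0.30. That is a high risk of a false stop if ordinary chemotherapy toxicity is common.

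**The case against.** The strongest reply is that criterion 4 is meant for manageable chemotherapy toxicity. Its second sentence names nausea, vomiting and hematologic events. Its four weeks match the limit in 11.6 for holding ramucirumab before a subject leaves study treatment. On that view a test that presupposes a dose change or delay simply does not apply to a permanent stop, and the discontinuation wording in criterion 1 keeps its effect. This reading is possible, but it is not written down. It does support keeping the condition for other toxicity.

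A reader might infer that the synopsis flatly contradicts 11.6.1. The documents do not go that far. The synopsis refers to dose modification and adequate treatment in garbled form, and may be a shortened version of criterion 4. What stands is that it states no explicit recovery test, so the two places can classify one event differently.

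A reader might also infer that the recovery condition cuts the chance of stopping a toxic regimen from 86.6% (no recovery) to 8.5% (half recover). That contrast applies 0.40 to all Grade ≥3 events, whereas 11.6 and 11.6.1 attach it to excessive toxicity as defined, criterion 4 included. On those terms a true rate of 0.40 reaches the boundary 86.6% of the time. The recovery shares are also assumed, and most of the drop comes from ordinary recovering toxicity. The 11.6.2 limits do not show that 0.20 and 0.40 were set for all events, because they concern single event types at one early look.

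Nor would serious events go unseen. Sections 10.2.2.1 to 10.2.2.3 require SAE reports within 24 hours and sponsor-investigator review. Section 12.1 provides monthly summaries, and section 12.2 gives annual DSMC review of aggregate events with escalation of immediate concerns. None of these carries a numerical boundary.

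**Conclusion.** The point holds as a gap in the definition. Taken literally, 11.6.1 can leave out a related first-cycle event that permanently ended ramucirumab/placebo and then recovered, and nothing in the text exempts it. It would be too strong to say that such events are certainly excluded, because the status of a permanent stop under criterion 4 is unclear.

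The numerical effect is modest and rests on assumptions. With a 40% first-cycle rate and a tenth of recovered events falling under 6.1.6, the chance of stopping by 40 subjects rises by about 5 percentage points when a quarter or half of events recover, and by under 1 point when three quarters do. The case for acting is patient safety at low cost, and a stopping rule whose count does not depend on who reads it.

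**What to change.** Add to the fourth criterion in 11.6.1: *This criterion does not apply to an event requiring permanent discontinuation under 6.1.6, or to a death; these count at onset.* For deaths this is clarification only, since a fatal event does not fall to grade 1. Put the same definition in the synopsis. Keep the recovery condition for other manageable chemotherapy toxicity.

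The cost is an amendment to two paragraphs, with no added subjects, visits or tests. The downside is a slightly higher chance of an early stop. Counting these events at onset also removes a wait of at least four weeks, during which about 85/24 × 28/30.44 = 3.3 further subjects would enrol at the planned rate.

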## 11.6.2 Interim Safety Analysis

The study will be closed to accrual and an interim safety analysis conducted after ten subjects are accrued to each arm. If the following rates of selected toxicities listed below are observed within the first cycle of treatment (four weeks), the regimen (Ramucirumab, Oxaliplatin, Irinotecan, 5-FU) will be considered toxic and the trial will be stopped.

Adverse Event (≥ grade 3)	Toxicity Rate (n/10 subjects)
Febrile Neutropenia	2/10
Peripheral Motor or Sensory Neuropathy	3/10
Hypertension	3/10
Life Threatening Thromboembolic Event	3/10
GI Perforation	2/10
Hemorrhage, Bleeding	2/10

Version Date: 13AUG2018 Confidential Page 42 of 51

#### 11.7 Interim Analysis for Efficacy

An interim analysis with the Kaplan-Meier method and logrank test will be conducted after 23 subjects have been enrolled in each arm and followed up for 9 months. The trial will stop if it detects a significant difference in PFS between the two arms at the significance level of 0.0013 according to the O'Brien-Fleming approach. Otherwise the trial will continue until the targeted sample size has been completed.

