# 11.4 Analysis Plan for Primary Objective

PFS will be estimated for each arm using the method of Kaplan and Meier. Nine month PFS will be reported along with a 95% confidence interval. PFS will be compared between Arm A and Arm B using a one-sided logrank test. The ITT analysis dataset will be used for this analysis.

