## 11.10 Sample Size/Accrual/Study Duration

We aim to test the null hypothesis of PFS at 6 months. Using a one-sided log-rank test we have estimated a sample size of 85 patients (43 in one and 42 in another arm) which will provide 80% power under a type 1 error of 20%. This is an estimation on 24 months accrual and 9 months follow up after accrual for the primary endpoint. Sample size may increase to 95 to account for a 10% drop out rate.

The expected progression free survival for mFOLFIRINOX in metastatic pancreatic cancer is 6 months. The addition of RAM to mFOLFIRINOX would be expected to increase the median PFS to at least 9 months. We assume a type 1 error ( $\alpha$ ) of 0.2 and a power (1- $\beta$ ) of 80%.

With an exact power of 0.8014, hazard ratio of 0.6667 and endpoint of detecting 3 months PFS advantage of the mFOLFIRINOX/ramucirumab combination over mFOLFIRINOX alone (from 6 to 9 months), the sample size on each arm was calculated to be 43 in the control arm and 42 in the treatment arm (total is 85). 29.30

The estimated enrollment period for this study is 24 months and the estimated study duration is 33 months.

Version Date: 13AUG2018 Confidential Page 43 of 51

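### The interim efficacy level of 0.0013, its attribution to O'Brien-Fleming and the one-sided 20% type 1 error do not agree; the effect is conservative, but the stopping rule needs restating.

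*Combined protocol and SAP*

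**What the plan says.** Section 11.7 places one efficacy look, by Kaplan-Meier and logrank test, which "will be conducted after 23 subjects have been enrolled in each arm and followed up for 9 months". The trial stops on "a significant difference in PFS between the two arms at the significance level of 0.0013 according to the" O'Brien-Fleming approach; otherwise it continues to full size. The synopsis (Statistical Considerations) gives the same level, "as compared to the standard arm-mFOLFIRINOX at the significance level of 0.0013 according to the" same approach, but words the trigger differently: "The trial will stop if it detects a significant difference of 3 months in PFS between the study arm-mFOLFIRINOX/RAM". Section 11.7 has no 3-month condition.

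For the final analysis, section 11.4 says "PFS will be compared between Arm A and Arm B using a one-sided logrank test". Section 11.10 gives the sample size of 85, "which will provide 80% power under a type 1 error of 20" per cent, and adds: "Sample size may increase to 95 to account for a 10% drop out rate".

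The plan does not give the expected number of events at the look, the information fraction, the form of O'Brien-Fleming boundary, the sidedness of 0.0013, or the level of the final test once the look has been taken.

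**The concern.** O'Brien-Fleming is not a free-standing number. Its interim level follows from the overall alpha and the fraction of information available at the look. With an overall one-sided alpha of 0.20 and a look near mid-information, that level should be several per cent. A level of 0.0013 is far below that.

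The named method and the stated number are therefore two different stopping rules. At N = 85, a one-sided p-value of 0.03 at the look would stop the trial under O'Brien-Fleming at alpha 0.20 in every timing considered below, and would continue it under 0.0013. The two rules also imply different final levels: effectively 0.20 with 0.0013, and about 0.17 to 0.19 with O'Brien-Fleming at alpha 0.20.

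**Working it through.** **Inputs.** From section 11.10: medians 6 and 9 months, hazard ratio 0.6667, type 1 error 0.20, 43 control and 42 treatment subjects, 24 months of accrual, 9 months of follow-up. From section 11.4: one-sided test. From section 11.7: 23 subjects per arm, 9 months of follow-up, level 0.0013. My assumptions: exponential PFS, uniform accrual, no dropout. All event counts are expectations.

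**1. Reproduce the design.** Schoenfeld events = 4(0.8416 + 0.8416)² / (ln 1.5)² = 69, or N of about 84. Freedman's formula gives 71 events, N of about 86. With N = 85 the event probabilities at month 33 are 0.8805 (control) and 0.7721 (treatment), so expected events are 43 × 0.8805 + 42 × 0.7721 = 70.3. Power is Φ(½√70.3 × ln 1.5 − 0.8416) = 0.805, against the stated 0.8014. A two-sided 0.20 test would need N of about 133 to 137. The design is therefore one-sided at 0.20.

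**2. Events at the look (N = 85).** The 46th subject enters at 46/85 × 24 = 13.0 months, so the look falls at about month 22, when 85 × 22.0/24, or about 78, subjects are enrolled. Section 11.7 allows three readings of which data count:
- Exactly 9 months per subject: 23 × (0.646 + 0.500) = 26.4 events, fraction t = 26.4/70.3 = 0.375.
- The first 46 subjects with all follow-up to that date: 34.5 events, t = 0.491.
- Everyone enrolled by that date: 45.0 events, t = 0.64.

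**3. O'Brien-Fleming level at one-sided 0.20.** The spending form is 2[1 − Φ(1.2816/√t)]. The classical two-look form solves P(Z₁ > c/√t or Z₂ > c) = 0.20 with correlation √t.

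| t (N = 85) | Spending form | Classical form |
|---|---|---|
| 0.375 | 0.036 | 0.064 |
| 0.491 | 0.067 | 0.087 |
| 0.64 | 0.109 | 0.114 |

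At N = 95 the fractions are about 0.34, 0.43 and 0.58, and the levels run from 0.027 to 0.103.

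**4. Sensitivity.** I added 10% dropout, 6-month medians in both arms, and an accrual pause of 0 to 4 months at the safety review. The pause reflects section 11.6.2 ("The study will be closed to accrual and an interim safety analysis conducted after ten subjects are accrued to each arm"); its length is my assumption. Across these, expected events at the look are 25 to 53 and the level is 0.027 to 0.130. Reading the 20% as two-sided does not reach 0.0013 either: the classical two-sided interim level is 0.031 to 0.088.

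**5. What would produce 0.0013.** At alpha 0.20 the fraction would have to be 0.159 (about 11 events) in the spending form, or 0.079 (5 to 6 events) in the classical form. Conversely, at the N = 85 fractions, 0.0013 corresponds to an overall one-sided alpha of about 0.010 to 0.049 (spending) or 0.008 to 0.033 (classical).

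**6. Operating characteristics of 0.0013, taken as one-sided (z = 3.011), N = 85.**
- Overall alpha with a final test at 0.20: 0.2000 to 0.2001. This also held in every sensitivity scenario.
- Power: 80.46%, the same to two decimals as with no look.
- Observed hazard ratio needed, exp(−2 × 3.011/√events): 0.31, 0.36 and 0.41 at 26.4, 34.5 and 45.0 events.
- Chance of stopping at hazard ratio 0.667, 1 − Φ(3.011 − ½√events × ln 1.5): 2.4%, 3.4% and 4.9%. If 0.0013 is two-sided: 1.5 to 3.2%.

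**7. O'Brien-Fleming at alpha 0.20 for comparison (34.5 events, t = 0.491).** Spending form: 0.067 then 0.181 at the end, power 79.6%, chance of stopping 38.1%. Classical form: 0.087 then 0.170, power 79.1%, chance of stopping 43.3%.

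**The case against.** The strongest reply is that nothing is harmed. The stated level is stricter than the named method requires, type 1 error and power are essentially unaffected, and the look comes at about month 22, when about 78 of 85 subjects are already enrolled, so a look that rarely stops forgoes little saving in accrual. All of this stands, and it limits the weight of the point.

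It is also fair to say that the final level is not wholly obscure. The only overall test level in the plan is one-sided 0.20, and with 0.0013 at the look a final test at 0.20 is practically exact. Sidedness and final level are unstated rather than wrong.

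The information fraction is assumed here because the plan gives none. The conclusion is limited to the scenarios tried; non-exponential PFS and accrual patterns other than uniform with a pause were not examined.

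A reader might go further and infer where the mistake lies. One inference is that 0.0013 was carried over from a conventional design: the spending form at one-sided 0.025 gives 0.0013 at a fraction of about 0.485, close to 46/95 = 0.484. Another is that 0.0013 was chosen as a deliberately strict boundary and only the label is wrong. The documents support neither. They give no derivation and no stated intent, and 95% confidence intervals for reporting are not a test level.

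**Conclusion.** The point holds as an inconsistency: the number, the named method and the one-sided alpha of 0.20 cannot all be right. O'Brien-Fleming at that alpha gives about 0.036 to 0.114 at N = 85 and 0.027 to 0.103 at N = 95, under exponential PFS, uniform accrual and no dropout; the mismatch persisted in every scenario tried. Which element is the slip cannot be settled from the documents.

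A reader might infer that the interim look inflates the type 1 error or weakens the trial. It does not. What changes is how the look behaves: it is close to unable to stop at the design effect, whereas the named method would stop in roughly two trials in five at 34.5 events. This should be fixed because it is a decision threshold, but the consequence is small.

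The 3-month wording in the synopsis is a minor, separate inconsistency. It could be taken as a second stopping criterion, but it reads most naturally as a restatement of the 6-to-9-month target in section 11.10.

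**What to change.** In section 11.7 and the synopsis, the sponsor should state which element governs and make the text consistent, in one of two ways.

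(a) Keep 0.0013 as a fixed boundary. Drop the attribution to O'Brien-Fleming at alpha 0.20, or give the alpha and information fraction from which 0.0013 was derived. State that it is one-sided and that the final test is at one-sided 0.20. This costs two or three sentences, with no change in sample size and no material loss of power.

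(b) Keep O'Brien-Fleming at one-sided 0.20. Name the form, and compute the interim level at the observed event fraction with its matching final level (at a fraction of 0.49, the pairs in step 7 of the working). This is a design choice: power falls from about 80.5% to about 79 to 80%, and early stopping at a hazard ratio of 0.667 becomes much more likely.

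Under either option, define which subjects and events enter the look, and say whether the 3-month difference in the synopsis is a condition for stopping or a restatement of the design target.
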